**Objectives:**

We propose to determine the effects of lipolytic inhibition on GH secretion in obese children as compared to the effects of such inhibition on GH secretion in short healthy children who are undergoing growth hormone stimulation testing. We plan to use our findings to better elucidate the

pathophysiology underlying diminished GH secretion in obesity as well as to pilot an improved testing of GH deficiency in overweight children.

### **Specific Hypotheses:**

In the course of this study we will test the following hypotheses:

- Inhibition of lipolysis by niacin will lead to a decrease in plasma FFA in obese and control children without inducing significant adverse effects.
- In the control group of short children (that are not found to be growth hormone deficient) peak stimulated GH concentration will be significantly greater than that observed in obese children. GH secretion of non-obese short children will be significantly augmented by niacin treatment.
- In obese children, peak stimulated GH concentration will be blunted after placebo but with niacin these measurements will increase significantly to achieve values similar to those seen in the non-GH-deficient control subjects after placebo.

### **Study Design and Methods:**

#### Inclusion Criteria:

Subjects will qualify for the overweight group (for the dose-establishing studies 1 and 2 and main study) if they meet the following criteria:

1. Good general health.
2. Age  $\geq 7$  and  $< 15$  years.
3. Tanner stage I, II, or III for the breast among girls and testes  $< 10$  mL for boys based upon an examination by a trained physician or nurse practitioner.
4. Weight  $> 30$  kg.
5. Fasting plasma glucose  $< 100$  mg/dL, 2 hour post-dextrose glucose  $< 140$  mg/dL, and HgbA1C  $\leq 6.4\%$ .

6. Females who are age 10 or greater must have a negative pregnancy test.
7. Body mass index  $\geq$  95th percentile determined by Centers for Disease Control age and sex specific data (given that most pathology of obesity does not usually emerge until children cross the 95th percentile).
8. No evidence of growth failure as defined as height  $>$  5th percentile.

Subjects will qualify for the non-overweight control group (for the main study only) if they meet the following criteria:

1. Recommended by a pediatric endocrinologist to undergo GH stimulation testing to establish the diagnosis of GH-deficiency.
2. Good general health.
3. Age  $\geq$  7 and  $<$  15 years.
4. Tanner stage I, II, or III for the breast among girls and testes  $<$  10 mL for boys based upon an examination by a trained physician or nurse practitioner.
5. Weight  $>$  30 kg.
6. Fasting plasma glucose  $<$  100 mg/dL, 2 hour post-dextrose glucose  $<$  140 mg/dL, and HgbA1C  $\leq$  6.4%.
7. Females who are age 10 or greater must have a negative pregnancy test.
8. Height  $<$  5th percentile.
9. BMI between the 5th and 85th percentiles determined by Centers for Disease Control age and sex specific data.
10. Birth weight and length not consistent with small for gestational age (SGA) criteria or a history of intrauterine growth restriction (IUGR) based on recall history.

Exclusion criteria (for the dose-establishing studies 1 and 2 and the main study):

Subjects will be excluded if they have any of the following:

1. Baseline creatinine  $\geq$  1.0 mg/dl.

2. Significant cardiac or pulmonary disease likely to or resulting in hypoxia or decreased perfusion.
3. Hepatic disease with elevated liver function tests (ALT or AST)  $\geq 1.5$  the upper limits of normal.
4. Pregnancy.
5. Evidence for impaired glucose tolerance or Type 2 diabetes, including fasting plasma glucose  $\geq 100$  mg/dL, 2 hour post-dextrose glucose  $\geq 140$  mg/dL, or HgbA1C  $> 6.4\%$ .
6. Presence of other endocrinologic disorders leading to obesity (e.g. Cushing Syndrome).
7. Any disorder that is known to affect GH secretion (e.g. untreated hypothyroidism) or use of any medication known to affect GH levels (including glucocorticoids and GH itself).
8. Any other disorder that is known to affect stature including skeletal dysplasias.
9. Recent use (within two years) of anorexiants, stimulant medications, or other medications felt to impact growth.
10. Individuals who have, or whose parent or guardians have, current substance abuse or a psychiatric disorder or other condition that, in the opinion of the investigators, would impede competence or compliance or possibly hinder completion of the study.
11. Individuals receiving medical treatment other than diet for hypertension or dyslipidemia.
12. Individuals with evidence of precocious puberty as defined as palpable breast tissue noted in females before the age of 7, testicular size  $\geq 4$ cc in males before the age of 9, or bone age advancement more than 2 SD for chronologic age.
13. Individuals receiving androgen or estrogen hormone therapy.

Each subject will receive a written explanation of the purposes, procedures, and potential hazards of the study. Communication of this information and of the subject's assent as well as the consent of the parent or guardian will be documented in the medical record. All subjects will be

informed of their right to withdraw from the study. Prior to blood draws subjects will be offered application of ELA Max cream to the surface of the skin for a minimum of one-half hour, to anesthetize the skin surface.

**Procedures of the study:**

Initial Screening Evaluation for the dose-establishing studies 1 and 2 and the main study:

Performed in the outpatient clinic. Study subjects will be screened at the Clinical Center in Bethesda.

1. **Protocol review and signing of consent and assent forms.** All study procedures will be discussed and study risks and benefits explained.
2. **Complete medical history and physical exam** with Tanner pubertal staging, weight (in kg), and height (in cm) by stadiometer (3 repeated measures).
3. **Fasting Blood Work** including fasting insulin and glucose concentrations, and fasting lipid profile to include total cholesterol, LDL, HDL, and triglycerides.
4. **Additional blood tests** for complete blood count, HgbA1C, electrolytes, renal, mineral, and hepatic profiles, thyroid functions, gonadotropins, testosterone and SHBG, IGF-1, IGF binding protein 3 (IGFBP-3), sedimentation rate, total IgA, tissue transglutaminase (TTG) IgA, iron, vitamin D, urinalysis, and research samples to be saved (10 mL) for future genetic analyses of genes important for obesity and/or GH deficiency. Urine pregnancy test for all females age 10 and over.
5. **Glucose tolerance test:** Following the fasting blood work, an oral dextrose solution (75 g per 300 mL) will be administered in a dose of 1.75 g of dextrose per kg of body weight up to a maximum dose of 75 g. Two hours after this administration blood glucose and insulin levels will be drawn.
6. **Bone age X-ray** as part of the evaluation for pubertal development. The bone age is considered a more objective measure of pubertal staging, especially in obese children where the ability to

determine sexual maturation by physical exam can be compromised. The bone age is also useful for secondary analysis, including correlation of bone age, pubertal staging, growth hormone, and final height predictions. (This evaluation will not be performed in the dose-establishing study.)

7. **Hyperphagia questionnaire.** A hyperphagia questionnaire that was originally designed for and validated in children and adults with PWS will be administered to the caregiver of all child subjects and any adult subjects who still reside with a caregiver to assess hyperphagic behavior, drive, and severity (see Appendix E).

#### Dose-Establishing Study 1

Only subjects meeting the inclusion and exclusion criteria during the screening visit will be evaluated. For dose-establishing study 1, we tested 2 subjects with the 250 mg niacin dose given every 2 hours. Since we did not see appropriate suppression of FFA concentrations (<200 uEq/L), we increased the dose to 500 mg every 2 hours and tested five more subjects. Since we did not see consistent suppression of FFA below 200 uEq/L with 500 mg every 2 hours, we will conduct another dose-establishing study lasting four hours, where niacin will be administered hourly (4 doses of 500 mg – see below). We will update the IRB on the results of dose-establishing study 2 before we initiate the main study.

The dose-establishing study visit 1 occurred within two months of screening visit to ensure consistency of physical exam and medical history throughout the study period. Patients were admitted the night before the first day of testing. Additionally, literature suggests that several vitamins influence growth hormone secretion; thus, if applicable, vitamin supplements were discontinued for three days prior to admission. All subjects were admitted to the NIH Clinical Center for an evaluation that included:

1. **Medical History and Physical Examination** with Tanner pubertal staging and anthropometric measurements including weight (in kg) and height (in cm) by stadiometer (3 repeated measures).
2. **Placement of an intravenous line** to be used for medication administration and blood sampling over a 24 hour time period.
3. **Repeat urine pregnancy test** in girls age 10 and older.
4. **Overnight Fast** beginning at 10 pm and ending after completion of testing the following day.
5. **Administration of niacin:** For dose-establishing study 1, niacin was given at 6am, 8am, and 10am. Each dose was either 250 mg or 500 mg as described above.
6. **Frequent blood sampling** from an indwelling intravenous line just prior to the first dose of niacin and then every 30 minutes for the next six hours. After completion of this sampling, the subjects were given an ad lib diet. Blood samples were analyzed for GHRH, somatostatin, GH, FFA, glucose (via bedside glucometer), and insulin concentrations. FFA assays were performed using the WAKO NEFA C diagnostic kit.
7. **Discharge:** Subjects were discharged following the completion of the frequent blood sampling.

### Dose-Establishing study 2

The dose-establishing visit for dose-establishing study 2 will occur within two months of screening visit to ensure consistency of physical exam and medical history throughout the study period. Patients will be admitted the night before the first day of testing. Additionally, literature suggests that several vitamins influence growth hormone secretion; thus, if applicable, vitamin supplements will be discontinued for three days prior to admission. All subjects will be admitted to the NIH Clinical Center for an evaluation that will include:

8. **Medical History and Physical Examination** with Tanner pubertal staging and anthropometric measurements including weight (in kg) and height (in cm) by stadiometer (3 repeated measures).
9. **Repeat urine pregnancy test** in girls age 10 and older.
10. **Overnight Fast** beginning at 10 pm and ending after completion of testing the following day.
11. **Placement of an intravenous line** to be used for medication administration and blood sampling over a 5 hour time period.
12. **Administration of niacin** at 7:30am, 8:30am, 9:30am, and 10:30am. Each dose will be 500 mg.
13. **Frequent blood sampling** from an indwelling intravenous line just prior to the first dose of niacin and then every 30 minutes for the next four hours. After completion of this sampling, the subject will be given an ad lib diet. Blood samples will be analyzed for GHRH, Somatostatin, GH, FFA, glucose (via bedside glucometer), and insulin concentrations. GHRH and Somatostatin will be sampled once per hour. Based on our first dose-establishing study, we believe that hourly samples for these two hormones will be sufficient to measure the changes that these hormones undergo during testing.
14. **Discharge:** Subjects will be discharged following the completion of the frequent blood sampling.

#### Main Study: Randomization

Only subjects meeting the inclusion and exclusion criteria during the screening visit will be randomized. Subjects will be assigned to receive placebo x 4 doses on the first day of GH stimulation testing and niacin 500 mg x 4 doses on the second day or they will be assigned to receive niacin 500 mg x 4 doses on the first day and placebo x 4 doses on the second day. Subjects

will be stratified by group and sex in blocks of 4 such that roughly equal numbers of subjects in each stratum will be assigned to each placebo and active medication administration order.

Additionally randomization of obese subjects will be stratified by BMI (95-99th percentile or >99th percentile).

Main Study: Inpatient evaluation:

Only subjects meeting the inclusion and exclusion criteria during the screening visit will be evaluated as inpatients. A total of 40 subjects in the two main groups will complete inpatient evaluation, although up to 50 may initiate inpatient evaluation in order to achieve full enrollment. The inpatient visit will occur within two months of screening visit to ensure consistency of physical exam and medical history throughout the study period. Patients will be admitted the night before the first day of testing. Additionally, literature suggests that several vitamins influence growth hormone secretion; thus, if applicable, vitamin supplements will be discontinued for three days prior to admission. All subjects will be admitted to the NIH Clinical Center for an evaluation that will include:

1. **Medical History and Physical Examination** with Tanner pubertal staging and anthropometric measurements including weight (in kg) and height (in cm) by stadiometer (3 repeated measures).
2. **DXA scanning** for determination of lean body mass and body fat mass.
3. **Placement of an intravenous line** to be used for medication administration and blood sampling over a 48 hour time period.
4. **Repeat urine pregnancy test** in girls age 10 and older.
5. **Overnight Fast** beginning at 10 pm on both nights; ending after completion of testing each day.
6. **Growth Hormone Stimulation testing** consisting of arginine (500 mg/kg IV up to maximum of 30 g, infused over 30 min) at 8:30am, followed by L-dopa (500 mg by mouth)

at 9:30am. A dose of niacin (dose determine in the dose-establishing study) or placebo will be administered by mouth at 7:30am, 8:30am, 9:30am, and 10:30am . The study will be repeated the next day in the same fashion. The order of niacin 500 mg or placebo will be randomized. Blood will be sampled from an indwelling intravenous line at times -60, -30, 0, +30, +45, +60 minutes of arginine infusion for measurements of GH, free fatty acids, glucose (via bedside glucometer), and insulin concentrations. Blood will also be sampled at times -30, 0, +30, +45, +60, +75, +90, and +120 minutes of L-dopa administration for the same serum concentrations. GHRH and Somatostatin will be sampled hourly at 7:30am, 8:30am, 9:30am, 10:30am, and 11:30am, with two additional measurements at +30 minutes (9am) of arginine infusion and +30 minutes (10am) of L-dopa administration. After completion of this sampling, the subject will be given an ad lib diet.

7. **Discharge:** Subjects will be discharged following the growth hormone stimulation test on the second day.

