**Table 2: Suppression of FFA <2 mEq/L by Niacin**

Group	Number of Subjects	Percentage of measurements post niacin with FFA <0.2 mEq/L
250 mg q 2H	2	11.5%
500 mg q 2H	5	43.1%
500 mg q 1H	5	67.5%

Adverse events during Dose Establishing Study 2 were largely as expected. All participants reported flushing or warmth, 60% tingling or rash, and 20-40% abdominal discomfort, nausea, or emesis.

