### **Randomization**

For randomizing order of administration of niacin and placebo, investigators will assign consecutive code numbers to participants from prespecified lists stratified by group, sex, and BMI (95-99th percentile or >99th percentile). The NIH Clinical Center Investigational Drug Management and Research Section will use permuted blocks with stratification to generate the allocations that translate code numbers into study group assignments by using a pseudo-random number program. Pharmacy personnel not otherwise involved with the conduct of the study will dispense study capsules in containers that appear identical and differ only by participant code number. No participant, investigator, or other medical or nursing staff interacting with participants will be aware of study group assignments during the trial.

Arginine hydrochloride 10% solution is approved by the FDA for growth hormone testing. This agent is available through the NIH pharmacy and is on the formulary. It will be used at a dose of 500 mg/kg IV up to maximum of 30g infused over 30 min on two consecutive days. This dosing corresponds to 5 mL/kg, with a maximum dose of 300 mL on two consecutive days.

L-dopa is not approved by the FDA for growth hormone testing, but is approved for other uses. L-dopa has been used clinically for many years for the purpose of growth hormone testing. L-dopa powder will be obtained from Spectrum Chemicals, which has supplied us with a Certificate of GMP. From 2011-2016, L-dopa was packaged, supplied, and distributed to the inpatient staff by the NIH pharmaceutical development section as 250 mg capsules. The analytical group of

Pharmaceutical Development Service conducted testing according to USP standards for medications used in this protocol prior to release for human consumption. Starting in mid-2017, Pine Pharmaceuticals will compound the 250 mg capsules and perform bioburden testing per the United States Pharmacopeia (USP) <61> and <62> standards. Purity and stability testing will be performed by the NIH Investigational Drug Management and Research Section, which will track and dispense all medications to the inpatient staff.

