### **Limitations to the Study Design**

**We have identified several possible limitations to our study, including:**

- 1) Given that the GH stimulation tests are being performed on consecutive days, it is possible that effects of the first day's testing could carry-over to the second day and affect the results. However, many studies in the adult literature have used similar study designs. Furthermore, Cavallo et al showed no difference in response to GH stimulation testing on two consecutive days. Additionally, by randomizing the order of placebo or niacin given during the stimulation tests, we believe any effects of order will be detected.
- 2) Niacin is known to cause flushing shortly after administration. We anticipate that this side effect may conceivably lead the subjects and investigators to become aware of which day the niacin and placebo capsules were administered. We do not believe the blinding is critical to the success of the study given that we are only measuring objective hormonal data.

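### A disclosed fixed block length of 4, combined with flushing that may reveal past orders, lets investigators foresee some children's treatment order; undisclosed varying block sizes would be a cheap, modest improvement

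*Combined protocol and SAP*

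**What the plan says.** Main Study: Randomization states that subjects "will be stratified by group and sex in blocks of 4 such that roughly equal numbers of subjects in" each stratum go to each administration order. It adds: "Additionally randomization of obese subjects will be stratified by BMI", at two levels. That makes six lists: two control (by sex) and four obese (sex by BMI level).

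The Randomization section under Pharmaceutical information divides the work. At the clinic, "investigators will assign consecutive code numbers to participants from prespecified lists stratified by group, sex, and BMI". The Investigational Drug Management and Research Section "will use permuted blocks with stratification to generate the allocations that translate code numbers into study group assignments", and pharmacy staff dispense identical-looking containers. Neither section mentions varying or undisclosed block sizes. The same section then says: "No participant, investigator, or other medical or nursing staff interacting with participants will be aware of study group assignments during the trial".

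The second item of Limitations to the Study Design says of niacin flushing that this "side effect may conceivably lead the subjects and investigators to become aware of which day the niacin and placebo capsules were administered". It accepts this because the outcomes are objective hormone measurements. The first item relies on randomised order to detect any effect of the first day's test on the second.

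On how often flushing occurs, the adverse-event summary for Dose-Establishing Study 2, which used the main study's four hourly doses, says: "All participants reported flushing or warmth". Data Table 3 shows flushing in 100% of those 5 children at hour 1.

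**The concern.** Permuted blocks conceal the next allocation only while past allocations stay masked or the block length stays unknown. Here the block length is printed in the investigators' working document, and the plan itself accepts that past orders may become visible. In a two-day crossover, knowing the niacin day is knowing the order. The absolute blinding statement and the limitations section therefore conflict.

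The plan's defence, that hormone measurements are objective, answers bias in measurement. It does not answer foreknowledge of the next child's order. If a coming order is known, the choice of which eligible child takes that place could depend on it. The niacin-first and placebo-first groups might then differ, and the carry-over safeguard needs them to be comparable. The primary model under Data Analysis names no period or sequence term, so balance between orders rests on the randomisation alone.

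**Working it through.** **Inputs.** Block length 4, allocated 1:1 (Main Study: Randomization). Six strata (same section). Fifty children studied, 25 per group (Determination of Sample Size). Flushing in 71% of children in the chart review (Risks and Discomforts, Niacin) serves as the low inference rate. The split over sex and BMI is not given. I assume near-even strata: control 12 and 13; obese 6, 6, 6 and 7.

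**The plan's own denominator.** 40 / (1 − 0.20) = 50, as stated.

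**Certain orders in a block of 4.** There are 6 equally likely arrangements of two niacin-first and two placebo-first. An order is certain once two earlier children in the block had the same order. By position:
- 1st and 2nd: 0
- 3rd: the first two agree in 2 of 6 arrangements, so 1/3
- 4th: always, so 1

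The sum is 4/3 per complete block.

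**Over the strata, with every earlier order inferred:**
- 12 children: 3 × 4/3 = 4.00
- 13 children: 4.00 + 0 = 4.00
- 6 children: 4/3 + 0 = 1.33; three such strata give 4.00
- 7 children: 4/3 + 1/3 = 1.67

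Total: 4.00 + 4.00 + 4.00 + 1.67 = 13.67 of 50 (27%). Simulation gives the same mean, with 95% of realised counts between 11 and 17. If stratum sizes vary at random, the mean is 14.2 (range 12.7 to 16.0).

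**Imperfect inference.** If each earlier order is inferred with probability q, certainty needs both children of the matching pair to be inferred, so the total is multiplied by q²:
- q = 0.9: 13.67 × 0.81 = 11.1
- q = 0.8: 13.67 × 0.64 = 8.7
- q = 0.71: 13.67 × 0.504 = 6.9

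Children assigned before the previous child in the stratum has been tested lower these further.

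**Mixed blocks of 4 and 6.** The same rule must be used for both designs: an order counts as certain if the full history, with the possible sizes known, leaves only one possibility. For example, after niacin-first, niacin-first, placebo-first, niacin-first at the start of a list, the block must be 6 and the last two orders are fixed. With every earlier order inferred, this gives about 3.4 of 50 by simulation (3.3 by exact calculation), or 7%. Concealed sizes would lower it further; that case was not computed.

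**Other properties, fixed 4 versus mixed 4/6.** Best-guess success is 68% versus 67%. The mean absolute imbalance between orders over the whole trial is 1.9 versus 1.7, with a 95th percentile of 4 in both.

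**The case against.** The strongest reply is that little follows from this. Every child receives both treatments, the primary outcome is the niacin-induced change by group, and no comparison by order is planned. Steering would need two eligible children in the same small stratum at once, and the eligibility criteria are mostly objective cut-offs. The documents do not say that the same people judge eligibility, book admissions and assign codes. This stands. A reader might infer that the niacin effect is biased or that allocation was manipulated; the documents support neither.

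The cue is also imperfect. The plan says only that unmasking may happen. The 100% rests on 5 children (exact 95% lower limit 48%), and 40% of them felt warm before any dose. Arginine, given on both days, can itself cause flushing, and the main-study symptom questionnaire is completed once, at the end of the stay. So 14 is a ceiling, not an expected count. Against that, the first capsule comes at 7:30am and arginine at 8:30am, so flushing in that first hour is not due to arginine.

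Nor do varying sizes abolish prediction. If the sizes are known, places predictable with at least 75% probability rise from 13.7 to 21.0. This also stands: the gain is in certainty only.

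Finally, the pharmacy section already generates the allocation, and eligibility must already precede randomisation. Both are true, but neither hides a printed block length from someone who has inferred past orders.

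**Conclusion.** The point holds as a minor weakness in allocation concealment. The documents contradict themselves on whether investigators can know assignments, and the disclosed block length turns that into possible foreknowledge. The ceiling is about 14 of 50 orders, or about 7 to 11 at inference rates of 0.71 to 0.9. These figures assume near-even strata and that each earlier child is tested before the next code in that stratum is assigned.

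The exposure is limited to the comparability of the two order groups, and so to the carry-over safeguard. The figures measure opportunity; they do not estimate bias in any outcome. The case for a change rests on its very low cost.

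**What to change.** - In Main Study: Randomization, delete the block length. State that permuted blocks of randomly varying size are used, with sizes held by the Investigational Drug Management and Research Section and not disclosed to investigators.
- Have that section regenerate the unused codes in the same six strata, for example with blocks of 4 and 6.
- In the Randomization section under Pharmaceutical information, state that a code is assigned only after the admission is booked.
- Reconcile that section's blinding statement with the limitations section: investigators may infer past orders from flushing, which is why block sizes are withheld.

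**Cost.** A few sentences and a rerun of the existing allocation program; no extra children, visits or procedures. Balance within a small stratum becomes slightly less exact: the largest possible difference is half the largest block, so 3 instead of 2. Overall order balance is unchanged.
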